17.2.3. Exploratory Biological studies

See Section 10 for full details on the exploratory biological studies.

17.3. Interim Analyses

No formal interim analysis for efficacy or futility will be performed. Data relating to DLTs (acute pattern grade II-IV GvHD) and other safety data will be reviewed on an ongoing basis by the statistician and CI and reviewed formally by the SRC prior to dose escalation/de-escalation decisions being made. Data will also be reviewed by the IDMC and the study may be stopped early if the incidence of DLTs or other toxicity is judged to be unacceptably high in the judgement of both the IDMC and the SRC.

18. ETHICAL CONSIDERATIONS

In conducting the trial, the Sponsor, UCL CTC and sites shall comply with all relevant guidance, laws and statutes, as amended from time to time, applicable to the performance of clinical trials including, but not limited to:

- the principles of Good Clinical Practice
- Human Rights Act 1998
- Data Protection Act 2018, and General Data Protection Regulation (EU)2016/679 (GDPR)
- Freedom of Information Act 2000
- Human Tissue Act 2004
- Mental Capacity Act 2005
- UK Policy Framework for Health and Social Care Research, issued by the Health Research Authority

18.1. Ethical Approval

The trial will be conducted in accordance with the World Medical Association Declaration of Helsinki entitled 'Ethical Principles for Medical Research Involving Human Subjects' (1996 version) and in accordance with the terms and conditions of the ethical approval given to the trial.

The trial has received a favourable opinion from the Research Ethics Committee (REC) and Health Research Authority (HRA) approval for conduct in the UK.

UCL CTC will submit Annual Progress Reports to the REC, commencing one year from the date of ethical approval for the trial.

18.2. Site Approvals

Evidence of assessment of capability and capacity by the Trust/Health Board R&D for a trial site must be provided to UCL CTC. Sites will only be activated when all necessary local approvals for the trial have been obtained.

18.3. Protocol Amendments

UCL CTC will be responsible for gaining ethical approval for amendments made to the protocol and other trial-related documents. Once approved, UCL CTC will ensure that all amended documents are distributed to sites as appropriate.

Site staff will be responsible for acknowledging receipt of documents and for implementing all amendments promptly.

18.4. Patient Confidentiality & Data Protection

Patient and donor identifiable data, including initials and date of birth will be collected by UCL CTC. UCL CTC will preserve patient confidentiality and will not disclose or reproduce any information by which patients could be identified. Data will be stored in a

secure manner and UCL CTC trials are registered in accordance with the Data Protection Act 2018 and GDPR, with the Data Protection Officer at UCL

In addition certain identifiable information will be held on file at the central laboratory where the Tem cells are manufactured. This is necessary in order to ensure the correct Tem cells are matched to the correct patient. The information that will be used by the central lab will be: the patient's name, date of birth and trial number, and the donor's name, date of birth and hospital number. The study team at UCL CTC will not have access to these identifiers. Patients and donors will be informed of this on the trial information sheets and asked to consent for their identifiers to be used.

19.2. Indemnity

University College London holds insurance against claims from participants for injury caused by their participation in the clinical trial. Participants may be able to claim compensation if they can prove that UCL has been negligent. However, as this clinical trial is being carried out in a hospital, the hospital continues to have a duty of care to the participant of the clinical trial. University College London does not accept liability for any breach in the hospital's duty of care, or any negligence on the part of hospital employees. This applies whether the hospital is an NHS Trust or otherwise.

Participants may also be able to claim compensation for injury caused by participation in this clinical trial without the need to prove negligence on the part of University College London or another party. Participants who sustain injury and wish to make a claim for compensation should be advised to do so in writing in the first instance to the Chief Investigator, who will pass the claim to the Sponsor's Insurers, via the Sponsor's office.

Hospitals selected to participate in this clinical trial shall provide clinical negligence insurance cover for harm caused by their employees and a copy of the relevant insurance policy or summary shall be provided to University College London, upon request.

20. FUNDING

The Medical Research Council (MRC) is supporting the central coordination of the trial through UCL CTC.

Research A and B costs will be reimbursed to sites as per the finance section of the mNCA.

21. PUBLICATION POLICY

Results of this trial will be submitted for publication in a peer reviewed journal. The manuscript will be prepared by the Trial Management Group and authorship will be determined by mutual agreement. Any secondary publications and presentations prepared by investigators must be reviewed by the TMG and must not be published prior to the first publication by the TMG.

Data generated by the study belong to the Sponsor, University College London. Participating sites may not publish trial results prior to the first publication by the TMG or without prior written consent from the TMG. Please refer to the model non-commercial agreement (mNCA) between the Sponsor and Site gives further information on intellectual property rights.

The ClinicalTrials.gov number should be quoted in any publications resulting from this trial.

Appendix 1 ABBREVIATIONS

AE	Adverse Event
ALP	Alkaline phosphatase
ALT	Alanine transaminase
ANC	Absolute Neutrophil Count
AR	Adverse Reaction
AST	Aspartate aminotransferase
ATIMP	Advanced Therapy Investigational Medicinal Products
CCGTT	Centre for Cell, Gene and Tissue Therapeutics
CI	Chief Investigator
CR	Complete Response
CRF	Case Report Form
СТ	Computerised Tomography
CTCAE	Common Terminology Criteria for Adverse Events
DFS	Disease Free Survival
DI	Designated Individual
DIS	Donor Information Sheet
DLI	Donor Lymphocyte Infusion
DPA	Data Protection Act
DLT	Dose-Limiting Toxicity
ECG	Electrocardiogram
ECOG	Eastern Cooperative Oncology Group
EDTA	Ethylene Diamine Tetra Acetate
EFS	Event Free Survival
FBC	Full Blood Count
GDPR	General Data Protection Regulation
GFR	Glomerular Filtration Rate
GvHD	Graft versus Host Disease
aGvHD	Acute Graft versus Host Disease
cGvHD	Chronic Graft versus Host Disease
HIV	Human Immunodeficiency Virus
HLA	Human leukocyte antigen
HRA	Health Research Authority
HTA	Human Tissue Authority
ICF	Informed Consent Form
ICH GCP	International Conference of Harmonisation-Good Clinical Practice
IDMC	Independent Data Monitoring Committee
IMP	Investigational Medicinal Product
IV	Intravenous
	Laciale Denydrogenase
	Liver Function Tests
	Lower Limit of Normal Medical Research Council
	Medical Research Council Megnetic Research Council
	Magnetic Resonance image
	National Canaar Bagaarah Instituta
	Nauonai Gancer Research Institute
	Non-relapse monality
ГD	Periprieral Blood

PD	Progressive Disease
PI	Principal Investigator
PIS	Patient Information Sheet
PMG	Project Management Group
PO	By mouth
PR	Partial Response
REC	Research Ethics Committee
RP2D	Recommended Phase II Dose
SAE	Serious Adverse Event
SAR	Serious Adverse Reaction
SCT	Stem Cell Transplant
SD	Stable Disease
SLA	Service Level Agreement
SRC	Safety Review Committee
SSA	Site Specific Assessment
SUSAR	Suspected Unexpected Serious Adverse Reaction
TEM	Effector Memory T cells
TCR	T Cell Receptor
TMF	Trial Master File
TMG	Trial Management Group
TSC	Trial Steering Committee
UCL CTC	CR UK and UCL Cancer Trials Centre
U&E	Urea and Electrolytes
ULN	Upper Limit of Normal
WBC	White Blood Cells
WOCBP	Woman of Childbearing Potential

Appendix 2 QUICK REFERENCE GUIDE TO PATIENT VISITS

Assessment/ procedure	Pre-Regi (within 4 w to registra	istration veeks prior ation)	CD62L-Tem Apheresis (Day of apheresis or up to 7 days after)	Pre- Tem Treatment (within 2 days prior to Tem infusion)	DLT Period Follow Up every 14 days (+/- 4 days) until 72 days post Tem infusion	Follow Up - D+100 - D+180 - D+270 - D+360 (+/- 10 days)	Footnotes
	Patient	Donor	Donor	Patient	Patient	Patient	1. Required for trial eligibility. Scans/procedures may take place greater than 4 weeks prior to
Demographic data	x	х					registration however current disease status must be confirmed at registration
Medical history	х						2 Biochemistry: Sodium potassium urea
Disease assessment (as per local policy)	x ¹					х	creatinine, calcium, phosphate, albumin, total
Haematopoietic Cell Transplantation Specific Co- morbidity Index	х						protein, bilirubin, AST, ALT, alkaline phosphatase and GFR
Physical examination & weight	x			х	х	х	6.4.1)
Echocardiogram or MUGA scan	х						4. HIV (Anti-HIV-1, 2 & HIV-1 & 2 RNA PCR),
Eligibility for CD62L ⁻ Tem infusion				х			Hepatitis B (HBSAG, Anti HBC, HBV DINA), Hepatitis C (Anti-HCV-Ab, HCV RNA PCR), HTLV (HTLV 1&2), Syphilis
Full blood count + differential	х			х	х	x	
Biochemistry ²	х			х	х	х	10ml peripheral blood in EDTA during follow up
Urine or serum pregnancy test ³	х	х		х			6. 5ml peripheral blood in serum tube
Infectious Disease Screen ⁴		х	х				7. 25ml peripheral blood in Lithium heparin tube
Adverse Event Assessment (incl. GvHD)				х	х	x ⁹	8. 10ml peripheral blood in EDTA
Lymphocyte subset analysis (performed locally)						х	9. Adverse Reactions required during follow up
Exploratory blood for chimerism ⁵	х	х				х	10. Performed on D+100 and +360 only
Exploratory blood for alemtuzumab levels ⁶				х			
Exploratory blood for viral & immune reconstitution ⁷						х	
Exploratory blood for TCR ⁸						x ¹⁰	

Appendix 3 EXPECTED ADVERSE EVENTS (20-22)

The following AEs are commonly associated with CD62L⁻ Tem DLI and will be considered expected for this treatment:

- Fever
- Chills
- Hypotension
- GvHD (CTCAE v5.0 term: Immune system disorders other: GvHD)*
- Bone Marrow Hypocellular
- Aplastic crisis* (CTCAE v5.0 term: Blood & lymphatic system disorders other: pancytopenia)
- Neutropenia
- Anaemia
- Thrombocytopenia
- Vomiting

*Should this adverse event result in death, it should be considered expected for this procedure.

The following ARs are commonly associated with apheresis and will be considered expected in donors:

- Citrate-induced hypocalcaemia
- Vasovagal syncope
- Hypovolaemia (CTCAE v5.0 term: Metabolism & nutrition disorders other: hypovolemia)
- Hypotension Thrombocytopenia
- Deep vein thrombosis

The following ARs are also expected in donors who have placement of a central venous catheter:

- Bleeding
- Infection
- Air embolism
- Pneumothorax
- Cardiac arrhythmia

Appendix 4 RESPONSE CRITERIA

CLL and PLL - modified from Hallek et al.(33)

CR, CRi or PR for trial entry

CR (complete remission): all the criteria have to be met, and patients have to lack disease-related constitutional symptoms;

CRi is a category defined by failure to recover satisfactory counts but other criteria for CR are met;

PR (partial remission): at least two of the criteria of group A plus one of the criteria of group B have to be met; SD is absence of PD and failure to achieve PR.

Parameter	Group	CR*	PR	PD
Lymphadenopathy	А	None >1.5 cm	Decrease ≥50%	Increase ≥50%
Hepatomegaly	А	None	Decrease ≥50%	Increase ≥50%
Splenomegaly	А	None	Decrease ≥50%	Increase ≥50%
Blood lymphocytes	A	>4,000/µl	Decrease ≥50% from baseline	Increase ≥50% over baseline
Marrow	A	Normocellular, <30% lymphocytes, no B-lymphoid nodules	50% reduction in marrow infiltrate or B-lymphoid nodules	
Platelet count	В	>100.000/µl	>100.000/µl or increase ≥50% over baseline	Decrease of ≥50% from baseline secondary to CLL
Haemoglobin	В	>11.0g/dl	>11g/dl or increase ≥50% over baseline	Decrease of >2g/dl from baseline secondary to CLL
Neutrophils	В	>1,500/µl	>1,500/µl or >50% improvement over baseline	

Malignant lymphoma - from Cheson et al.(29)

CR or PR for trial entry

	Site	PET-CT-Based Response	CT-Based Response
		Complete metabolic response	Complete radiologic response (all of the following)
Complete Response	Lymph nodes and extralymphatic sites	Score 1, 2, or 3 with or without a residual mass on 5PS† It is recognized that in Waldeyer's ring or extranodal sites with high physiologic uptake or with activation within spleen or marrow (eg, with chemotherapy or myeloid colony-stimulating factors), uptake may be greater than normal mediastinum and/or liver. In this circumstance, complete metabolic response may be inferred if uptake at sites of initial involvement is no greater than surrounding normal tissue even if the tissue has high physiologic uptake	Target nodes/nodal masses must regress to ≤ 1.5 cm in long diameter No extralymphatic sites of disease
	Nonmeasured lesion	Not Applicable	Absent
	Organ enlargement	Not Applicable	Regress to normal
	New lesions	None	None
	Bone marrow	No evidence of FDG-avid disease in marrow	Normal by morphology; if indeterminate, IHC negative
		Partial metabolic response	Partial remission (all of the following)
Partial Response	Lymph nodes and extralymphatic sites	Score 4 or 5 [†] with reduced uptake compared with baseline and residual mass(es) of any size At interim, these findings suggest responding disease	 ≥ 50% decrease in SPD of up to 6 target measurable nodes and extranodal sites When a lesion is too small to measure on CT, assign 5x5 mm as the default value When no longer visible, 0 x 0 mm

ТоТет

		At end of treatment, these findings indicate residual disease	For a node > 5 x 5 mm, but smaller than normal, use actual measurement for calculation
	Nonmeasured lesion	Not Applicable	Absent/normal, regressed, but no increase
	Organ enlargement	Not Applicable	Spleen must have regressed by > 50% in length beyond normal
	New lesions	None	None
	Bone marrow	Residual uptake higher than uptake in normal marrow but reduced compared with baseline (diffuse uptake compatible with reactive changes from chemotherapy allowed). If there are persistent focal changes in the marrow in the context of a nodal response, consideration should be given to further evaluation with MRI or biopsy or an interval scan	Not applicable
		No metabolic response	Stable disease
No Response Or	Target nodes/nodal masses, extranodal lesions	Score 4 or 5 with no significant change in FDG uptake from baseline at interim or end of treatment	< 50% decrease from baseline in SPD of up to 6 dominant, measurable nodes and extranodal sites; no criteria for progressive disease are met
Stable Disease	Nonmeasured lesions	Not Applicable	No increase consistent with progression
	Organ enlargement	Not Applicable	No increase consistent with progression
	New lesions	None	None
	Bone marrow	No change from baseline	Not Applicable
Progressive		Progressive metabolic disease	Progressive Diseased requires at least 1 of the following PPD progression:
0136436	Individual target nodes/nodal masses	Score 4 or 5 with an increase in intensity of	An individual node/lesion must be abnormal with:

Extranodal lesions	uptake from baseline and/or New FDG-avid foci consistent with lymphoma at interim or end-of- treatment assessment	LDi > 1.5 cm and Increase by \ge 50% from PPD nadir and An increase in LDi or SDi from nadir 0.5 cm for lesions ≤ 2 cm 1.0 cm for lesions > 2 cm In the setting of splenomegaly, the splenic length must increase by $> 50\%$ of the extent of its prior increase beyond baseline (e.g., a 15-cm spleen must increase to > 16 cm). If no prior splenomegaly, must increase by at least 2 cm from baseline New or recurrent splenomegaly
Nonmeasured lesions	None	New or clear progression of pre- existing nonmeasured lesions
New lesions	New FDG-avid foci consistent with lymphoma rather than another etiology (eg, infection, inflammation). If uncertain regarding etiology of new lesions, biopsy or interval scan may be considered	Regrowth of previously resolved lesions A new node > 1.5 cm in any axis A new extranodal site > 1.0 cm in any axis; if < 1.0 cm in any axis, its presence must be unequivocal and must be attributable to lymphoma Assessable disease of any size unequivocally attributable to lymphoma
Bone marrow	New or recurrent FDG- avid foci	New or recurrent involvement

Abbreviations: 5PS, 5-point scale; CT, computed tomography; FDG, fluorodeoxyglucose; IHC, immunohistochemistry; LDi, longest transverse diameter of a lesion; MRI, magnetic resonance imaging; PET, positron emission tomography; SDi, shortest axis perpendicular to the LDi; SPD, sum of the product of the perpendicular diameters for multiple lesions.

*A score of 3 in many patients indicates a good prognosis with standard treatment, especially if at the time of an interim scan. However, in trials involving PET where de-escalation is investigated, it may be preferable to consider a score of 3 as inadequate response (to avoid undertreatment). Measured dominant lesions: Up to six of the largest dominant nodes, nodal masses, and extranodal lesions selected to be clearly measurable in two diameters. Nodes should preferably be from disparate

regions of the body and should include, where applicable, mediastinal and retroperitoneal areas. Non-nodal lesions include those in solid organs (e.g., liver, spleen, kidneys, lungs), GI involvement, cutaneous lesions, or those noted on palpation. Nonmeasured lesions: Any disease not selected as measured, dominant disease and truly assessable disease should be considered not measured. These sites include any nodes, nodal masses, and extranodal sites not selected as dominant or measurable or that do not meet the requirements for measurability but are still considered abnormal, as well as truly assessable disease, which is any site of suspected disease that would be difficult to follow quantitatively with measurement, including pleural effusions, ascites, bone lesions, leptomeningeal disease, abdominal masses, and other lesions that cannot be confirmed and followed by imaging. In Waldeyer's ring or in extranodal sites (e.g., GI tract, liver, bone marrow), FDG uptake may be greater than in the mediastinum with complete metabolic response, but should be no higher than surrounding normal physiologic uptake (e.g., with marrow activation as a result of chemotherapy or myeloid growth factors).

[†]PET 5PS: 1, no uptake above background; 2, uptake \leq mediastinum; 3, uptake > mediastinum but \leq liver; 4, uptake moderately > liver; 5, uptake markedly higher than liver and/or new lesions; X, new areas of uptake unlikely to be related to lymphoma.

Lymphoplasmacytic lymphoma and Waldenstrom's macroglobulinaemia -

from Owen et al.(30)

CR, VGPR or PR for trial entry

Response	Definition
Complete response (CR)	Absence of serum monoclonal IgM protein by immunofixation Normal serum IgM level Complete resolution of extramedullary disease, i.e., lymphadenopathy and splenomegaly if present at baseline Morphologically normal bone marrow aspirate and trephine biopsy
Very good partial response (VGPR)	Monoclonal IgM protein is detectable ≥90% reduction in serum IgM level from baseline* Complete resolution of extramedullary disease, i.e., lymphadenopathy/splenomegaly if present at baseline No new signs or symptoms of active disease
Partial response (PR)	Monoclonal IgM protein is detectable ≥50% but<90% reduction in serum IgM level from baseline* Reduction in extramedullary disease, i.e., lymphadenopathy/splenomegaly if present at baseline No new signs or symptoms of active disease
Minor Response (MR)	Monoclonal IgM protein is detectable ≥25% but<50% reduction in serum IgM level from baseline* No new signs or symptoms of active disease
Stable Disease (SD)	Monoclonal IgM protein is detectable

	<25% reduction and <25% increase in serum IgM level from baseline* No progression in extramedullary disease, i.e., lymphadenopathy/splenomegaly	
	No new signs or symptoms of active disease	
Progressive Disease (PD)	≥25% increase in serum IgM level* from lowest nadir (requires confirmation) and/or progression in clinical features attributable to the disease	
*Sequential changes in IgM levels may be determined either by M protein quantitation by densitometry or total serum IgM quantitation by nephelometry.		

Myeloma - adapted from Rajkumar SV, Harousseau J-L, Durie B et al.(31)

CR, sCR, VGPR or PR for trial entry

The IMWG response criteria for myeloma should be used for defining response:

Complete remission (CR)	Negative immunofixation on serum and urine
	Disappearance of any soft tissue plasmacytomas
	<5% plasma cells in bone marrow
Stringent complete	As above and:
remission (sCR)	Normal SFLC ratio and no evidence of clonal plasma cells on immunohistochemistry or flow cytometry
Very good partial response (VGPR)	>90% reduction in serum paraprotein and <100mg/24h BJP
Partial response (PR)	>50% reduction in serum paraprotein and/or >90% reduction in BJP and/or ≥50% decrease in difference between involved and uninvolved SFLC and/or >50% decrease in bone marrow plasma cells (if non-secretory multiple myeloma)
Stable disease/no	None of the above and not progressive disease
response (SD)	Define the time to progression
Progressive disease (PD)	>25% increase in serum paraprotein (absolute increase >5g/L)
	Urinary BJP (absolute increase >200mg/24h)
	Difference between SFLC (absolute increase >100mg/L)
	Bone marrow plasma cells (absolute >10%)
	New bone lesions/plasmacytomas
	Myeloma-related hypercalcaemia
Primary refractory	Defined as having never achieved partial response on therapy (PR)
	Non-responding, non-progressive
	Progressive disease
Relapsed/refractory	Achieved partial response on therapy (PR) then progressed within 60 days
Relapsed	Developed progressive disease after initially achieving partial response with >60 days duration and occurs off therapy

AML and ALL - adapted from Cheson et al.(32)

CR or CRi for trial entry

Complete remission (CR)	The marrow is regenerating normal haematopoietic cells and contains <5% blast cells by morphology on the aspirate film. ANC ≥1.0 × 109/L; platelet count ≥100 × 109/L
CR with incomplete hematologic recovery (CR _i)	All CR criteria except for residual neutropenia (<1.0 × 109/L) or thrombocytopenia (<100 × 109/L)
Relapse	Not meeting criteria for CR or CRi

MDS and CMML

Note that response criteria are based upon eligibility of <10% blasts at study entry

Complete remission (CR)	The marrow is regenerating normal haematopoietic cells and contains <5% blast cells by morphology on the aspirate film. ANC ≥1.0 × 109/L; platelet count ≥100 × 109/L
CR with incomplete hematologic recovery (CR _i)	All CR criteria except for residual neutropenia (<1.0 × 109/L) or thrombocytopenia (<100 × 109/L)
Relapse	Not meeting criteria for CR or CRi

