The target population in this trial is patients undergoing an HLA-identical sibling haematopoietic stem transplant. The number of patients undergoing this procedure is 470/year in the UK, 5900/year in Europe and 2500/year in the US. The intended benefit of CD62L⁻ Tem transfer is to accelerate immune reconstitution in patients undergoing allo-SCT without incurring a greater risk of GvHD. Patients will therefore potentially benefit from improvements in clinical outcomes as a result of reduced non-relapse mortality secondary to infection. A reduction in hospital readmission and the need for additional treatments will help to improve the quality-of-life for patients. Reduced length-of-stay, re-admissions and drug costs could also reduce the financial burden to health care systems and increase value for money

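### Appendix 4, CLL/PLL: the CR lymphocyte limit runs the wrong way, and the PD lymphocyte limit has no defined baseline or disease attribution, so normal recovery can be read as progression

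*Protocol*

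**What the plan says.** **CLL/PLL table, Appendix 4, blood lymphocytes.**
- CR: a count above 4,000/µl.
- PR: "Decrease ≥50% from baseline".
- PD: "Increase ≥50% over baseline".

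The rule above the table makes every CR entry binding: "CR (complete remission): all the criteria have to be met". The platelet PD entry reads "Decrease of ≥50% from baseline secondary to CLL", and the haemoglobin PD entry carries the same attribution to CLL. The lymphocyte PD entry carries none. The appendix does not define baseline.

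**Waldenström table, Appendix 4.** PD is "≥25% increase in serum IgM level* from lowest nadir (requires confirmation"), and/or clinical progression. Only the clinical limb has to be attributable to the disease. The footnote lets IgM be followed by M-protein densitometry or by "total serum IgM quantitation by nephelometry".

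**Where these definitions are used.** Section 6.2.1 points to Appendix 4 for CR and PR at entry. Section 9.5 leaves disease assessment in follow-up to local policy. Section 17.2.2 counts relapse and progression as EFS events without citing Appendix 4. Section 8.6 releases patients who progress from the remaining visits up to day +360. Section 8.9 says that patients who progress after Tem stay in follow-up under 9.4 and 9.5.

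**Purpose of the infusion.** Section 2.1 says that the intended benefit "is to accelerate immune reconstitution in patients undergoing allo-SCT".

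**The concern.** CLL/PLL patients enter in CR, CRi or PR, receive alemtuzumab, and are then given cells meant to speed immune recovery. A progression rule based on a bare percentage rise in total lymphocytes cannot tell that recovery from returning disease. The platelet and haemoglobin rows include the condition that would make the distinction, and the lymphocyte row does not. The CR entry adds a contradiction: read literally, a patient with a normal count below 4,000/µl cannot be in CR, while lymphocytosis satisfies that row.

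At stake is the meaning of progression in these diseases. A false call can become a secondary EFS event, can end the scheduled visits at which immune-recovery samples are taken, and under 8.9 makes the patient eligible for additional therapy.

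**Working it through.** The plan gives no figure to reproduce. The check applies the printed limits as arithmetic and compares the cells.

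**1. Direction of the lymphocyte row.** PR is a fall of at least 50% and PD is a rise of at least 50%, so lower is better. A CR entry requiring more than 4,000/µl points the other way. All CR entries must be met, so the entry binds.

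**2. PD with a low baseline.** PD is met when count ≥ 1.5 × baseline. The protocol gives no counts, so these baselines are assumed:

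| Baseline (/µl) | PD from (/µl) | Still at or below 4,000? |
|---|---|---|
| 200 | 300 | yes |
| 500 | 750 | yes |
| 1,000 | 1,500 | yes |
| 2,000 | 3,000 | yes |
| 3,000 | 4,500 | no |

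The boundary is 4,000/1.5 = 2,667/µl. For any baseline up to that value, a count at or below the table's own 4,000/µl can meet PD. At the same baselines a count of 4,001/µl meets the printed CR entry and the PD entry together.

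**3. PD with a leukaemic baseline.** If baseline is the count before treatment, for example 10,000/µl (assumed), PD on this row starts at 1.5 × 10,000 = 15,000/µl. A relapse showing only in the blood count is not called until then. Neither reading serves a patient already in remission.

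**4. Effect of correcting the CR sign alone.** Reading 4,000/µl as an upper limit removes the overlap of CR and PD above 4,000/µl. Step 2 is unchanged, because it comes from the undefined baseline and the missing attribution.

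**5. Waldenström.** PD is met when IgM ≥ 1.25 × nadir. For assumed nadirs of 0.20 and 0.40 g/L, the limit is reached at 0.25 and 0.50 g/L, rises of 0.05 and 0.10 g/L. If total IgM is the measure, the rise need not be monoclonal. Confirmation does not remove the problem, since true recovery persists.

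**6. Weight of one false event on 1-year EFS.** With no censoring, and if the patient would otherwise be event-free at 1 year, the shift is 1/n:
- all 18 patients: 1/18 = 5.6 points
- a dose level of 6: 1/6 = 16.7 points
- a dose level of 2, the minimum at an open dose: 1/2 = 50 points

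Section 17.2.2 plans EFS both pooled and per dose level.

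**The case against.** The strongest reply is that the link from Appendix 4 to EFS is not written down. The appendix is cited for CR and PR at entry, its disease sections name the responses needed for entry, follow-up is by local policy, and the EFS definition does not mention it. This stands, and it limits the point to what can happen where a site applies these cells. It is not a full answer: the protocol defines progression for these diseases nowhere else, and PD entries serve little purpose if only CR, CRi and PR matter.

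Second, the PR entry measures a fall from baseline, which suggests a count before the response, and the Waldenström table shows that the authors separate nadir from baseline. On that reading ordinary recovery is not PD. This also stands, but it leads to the missed relapse of step 3. The table does not say, either, whether one PD entry is enough.

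Third, the CR sign may have been misread from the PDF. That is worth checking in the source file, although the marrow entry in the next row kept its less-than sign. If the sign proves correct in the source, that part falls and the PD part remains.

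Several stronger inferences are tempting, and the documents do not support them:
- *EFS is biased downwards in the patients in whom Tem works.* This needs both a low baseline and use of Appendix 4 in follow-up, and neither is stated. The progression exclusion in 6.2.3 comes before the infusion, so it cannot penalise a response to Tem.
- *Every CLL/PLL patient would be called progressive.* The protocol gives no counts, and the number of such patients among at most 18 is unknown and may be zero.
- *GvHD data are lost after progression.* Section 12.4 records all GvHD to day 360 with no exemption, and 8.9 keeps follow-up going.
- *The CR sign changes eligibility.* PR is also accepted, so a patient in remission who fails this one entry can still enter as PR.
- *IgM recovery is the intended effect.* Section 3.1 names T-cell reconstitution. IgM is not a direct effect of a T-cell product.
- *The 0.20 to 0.25 g/L patient is in CR and PD at once.* CR needs a normal IgM, and no normal range is given.

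**Conclusion.** The point holds within these limits. The CLL/PLL lymphocyte row contradicts itself on CR. Its PD entry lacks both a defined baseline and the attribution that neighbouring rows carry. With a baseline up to 2,667/µl, normal recovery can meet PD; with a leukaemic baseline, this row calls relapse too late. The Waldenström rule has a lesser form of the same fault, and only if total IgM is used.

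The size is one secondary EFS event per false call, about 5.6 points among 18 patients and more within a dose level. Required visits may also end under 8.6, which 8.9 contradicts. This assumes that the site uses Appendix 4 for progression, that one PD entry is enough, and that there is no censoring. EFS is secondary and descriptive. The DLT endpoint, the MTD and the dose-toxicity model do not depend on any of this.

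**What to change.** 1. In the CLL/PLL table, make the CR lymphocyte limit an upper limit.
2. Define baseline for the lymphocyte PD entry and add the attribution to CLL used for platelets and haemoglobin.
3. Make the Waldenström IgM criterion attributable to the disease, as its clinical limb already is.
4. State in 17.2.2 whether Appendix 4 or local policy defines progression for EFS.
5. Have the sponsor reconcile 8.6 with 8.9 on follow-up after progression.

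New thresholds, such as an absolute lymphocyte floor, a clonal B-cell requirement or an immunofixation rule, are not proposed here. Progression decides access to Tem and to later therapy, so such criteria are for the sponsor to settle.

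The cost is a few table edits and short clarifications. Lymphocyte subsets, including B cells, are already taken at each follow-up visit under 9.5 and can inform the attribution. The downside is small: attribution needs a judgement at the visit, so some relapses may be called slightly later.
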